4.1 Treatment Design

Type of Design: Open label; two group study with healthy controls

Screening/Baseline: Participants will undergo a general medical screening visit to include vital signs, physical exam and pregnancy test (if applicable), then proceed with spirometry.

Intervention/Treatment

Participants will inhale aerosolized radiolabeled sulfur colloid ($Tc99m$ -SC) and will undergo gamma scintigraphy to measure mucociliary and cough clearance (MCC/CC) of the radiolabeled particles from the airways in both groups. During the first hour of MCC imaging patients will attempt to avoid coughing. Patients will then inhale 4 puffs of albuterol (90 mcg/puff via metered dose inhaler (MDI) with spacer) to assess the effect of beta-adrenergic stimulation on MCC over the second hour of MCC

imaging. After the two hours of MCC imaging patients will perform spirometry and directed coughing over a 30 minute period during which CC will be measured, again by gamma scintigraphy. Subjects will then rest (app 3.5 hours) and be scanned for 15 minutes at 6 hour \pm 30 minutes post initial MCC/deposition scan.

Table of procedures

| PCD MCC/CC study flow sheet | minutes needed | cumulative min |
|---|----------------|----------------|
| 1 Vital signs, PE,pregnancy test, PFT | 30 | 30 |
| 2 Put Americium fiducial markers on | 5 | 35 |
| 2 Co57 Transmission scan | 5 | 40 |
| 3 Background scan | 15 | 55 |
| 4 Radioaerosol inhalation | 5 | 60 |
| 5 MCC scan (no cough) | 64 | 124 |
| 6 Albuterol MDI (4 puffs with spacer) | 6 | 130 |
| 7 MCC scan post albuterol | 54 | 184 |
| 8 PFT and directed coughing (30 coughs including any spontaneous induced by PFTs) | 20 | 204 |
| 9 CC scan post PFT/cough | 4 | 208 |
| 10 Rest until final scan 6 hours after beginning of #5 | 210 | 418 |
| 11 6 hour post initial radioaerosol MCC scan | 15 | 433 |

Unscheduled Visits: There is no expectation for unplanned visits. Subjects will simply be rescheduled if they have a change in health.

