9.1. Strategies that Apply to all the Specific Aims

To describe each measure of MCC by retention vs. time data set, the average % clearance (or 100* (1-Retention)) over the 0-60 and 60-120 min period of observation are computed (i.e. average of the 10 minute clearance values from 0 to 60 and 60-120 minutes). These computed values are signified as Ave60Clr and Ave120Clr respectively. Each calculated AveClr value utilizes all 10-minute data points, rather than simply reporting a clearance value at a single time, and represents the average clearance at the midpoint of each period of retention vs. time observation. 6 hour clearance is determined by (100* (1- 6 hour retention)) and provides an index of initial airway (6hr Clr) vs. alveolar (6hr retention) deposition that along with the central/peripheral (C/P) ratio provides regional deposition data that can be included as covariates in analysis of MCC comparisons between groups and within individuals.

Distributions of the outcomes is expected to be normal. We will plot the data in histograms and qqplot to evaluate any extreme datapoints or outliers. Their impact if any will be analyzed by performing the analysis with and without these datapoints.

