Aim 2: To characterize the effect of a short acting beta agonist (SABA) on MCC in PCD subjects with mutations in genes that are associated with mild or severe disease, and compare the 2 populations in terms of change in Average Clearance.

In aim 2, we will be measuring the effect of albuterol on MCC in PCD subjects. We will look at the change between Ave60Clear (before albuterol) and Ave120Clr (after albuterol) for each subject. Estimates of the means and standard deviations with associated confidence intervals will be reported for each group. Using paired t-tests, we will verify if the change is significantly different than 0. The difference between the 2 PCD groups will then be analyzed with an independent t-test. Age, gender and the initial deposition C/P will be added as covariates to PCD groups in a linear regression model on MCC.

As this is not a randomized crossover design nor a parallel-arm design, our proposed comparison pre- to post-albuterol is uncontrolled and cannot assess the efficacy of SABA. The goal of our study is to obtain first estimates of the immediate effect albuterol on MCC in a small, controlled population.

Aim 3: To characterize cough clearance in PCD subjects with mutations in genes that are associated with mild or severe disease, and compare the 2 populations in terms of change in Average Clearance.

We will compare cough clearance in PCD subjects with mutations associated with mild disease with PCD subjects with mutations in genes associated with more severe disease. Cough clearance will be measured as the change in retention between 120 and 150 min post deposition. This change between Ave120Clr and Ave150Clr will be tabulated for each PCD group in term of means and standard deviations with associated confidence intervals and compared to 0 using paired t-tests. The difference between the 2 PCD groups will then be analyzed with an independent t-test. Age, gender and the initial deposition C/P will be added as covariates to PCD groups in a linear regression model on MCC.

For all aims, all tests will be 2-sided, with $\alpha=0.05$. Tests with p values above 0.05 will be considered inconclusive.

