Expected results, potential problems, and alternatives. We expect to observe a significant rate of MCC (different from 0) in the group of PCD patients with mutations in genes associated with a milder phenotype. Based on previous studies of ciliary activity in PCD subjects with mutations associated with a more severe phenotype, we expect to see little or no MCC in this group of PCD patients. Further, we expect the rate of MCC to be significantly greater in subjects in the “mild genotype” group compared to the PCD patients in the “severe genotype” group. We expect that subjects with a mild genotype will respond to albuterol with an increase in MCC while the PCD patients with the severe genotype will not. We expect that subjects with mutations in genes associated with a mild phenotype will have better cough clearance compared to subjects with mutations in genes associated with a severe phenotype. As we have performed many similar studies in the past, including studies of MCC in PCD subjects, we anticipate no technical difficulties in carrying out these studies. If there is no difference detected between the groups of PCD patients, this would suggest that the less severe clinical phenotype observed in some patients is not due to the maintenance of a low level of MCC. Nevertheless, this would be an important experimental finding, as it would indicate that some other mechanism is responsible for the difference in phenotype.

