9.6. Sample Size Rationale

Sample size:

Based on the results of mucociliary transport (MCT) rates (healthy: 6.58 ± 1.39 , *Rspn1*^{-/-}: 1.63 ± 0.78 , other PCD: 0) in our mouse model [13], we expect subjects with a mild genotype to average 25% of the MCC of healthy subjects (healthy: Ave60Clr = $14.3 \pm 7.2\%$; mild expected: $3.6 \pm 2\%$), while subjects with a severe genotype will not show any MCC results, i.e. Ave60Clr not different from 0 (expected 0.5 ± 0.25). With $n=10$, we will be able to observe significant differences between all groups, with $\alpha=0.05$ and power=0.8.

Moreover, we expect the mild genotype group to react to albuterol treatment by doubling their Ave60 Clr, while the group with severe mutations will not. With 10 subjects, we will be able to find a significant response in the mild genotype group with expected Ave60Clr = $7.2 \pm 4\%$. Accounting for 20% possible dropout, we plan to enroll 12 subjects.

10. Safety Monitoring and Management

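### Aim 3 counts mucociliary clearance that continues during the cough window as cough clearance, which biases the mild-versus-severe comparison toward the expected result

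*Combined protocol and SAP*

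**What the plan says.** Section 9.3, Aim 3 defines the outcome in one sentence: "Cough clearance will be measured as the change in retention between 120 and 150 min post deposition". The next sentence makes it operational: "This change between Ave120Clr and Ave150Clr will be tabulated for each PCD group". Each group's change is tested against 0 with a paired t-test. Then "The difference between the 2 PCD groups will then be analyzed with an independent t-test", at two-sided alpha 0.05. The regression that follows has no term for MCC rate: "Age, gender and the initial deposition C/P will be added as covariates to PCD groups in a linear regression model on MCC".

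The expectations that matter are in two places. The expected-results paragraph of section 9.3 says "We expect that subjects with a mild genotype will respond to albuterol with an increase in MCC", foresees little or no MCC in the severe group, and predicts that the mild group will show the better cough clearance. Section 9.6 puts figures on this: Ave60Clr 3.6% (SD 2) in the mild group and 0.5% (SD 0.25) in the severe group, and "we expect the mild genotype group to react to albuterol treatment by doubling their Ave60 Clr, while the group with severe mutations will not".

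The table of procedures in section 4.1 (Treatment Design) runs the post-albuterol MCC scan, the spirometry and coughing, and the "CC scan post PFT/cough" one after another. There is no comparison interval without coughing.

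**The concern.** MCC does not stop when coughing starts. The change from 120 to 150 minutes is therefore the sum of what coughing clears and what the cilia clear in the same minutes. Where the second part is the same in both groups it cancels in the comparison. Here the plan's main hypothesis is that it is not the same.

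Two tests are affected. In the mild group, the test against 0 can reject with no cough effect at all. Between groups, the t-test can reject because MCC differs, which is what Aim 1 already examines. At stake is a statement that genotype affects cough clearance when the data may show only that genotype affects MCC. Section 9.3 warns that the albuterol comparison in Aim 2 is uncontrolled; Aim 3 carries no comparable caution.

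**Working it through.** **Planned figures.** Section 9.6 takes mild Ave60Clr as 25% of the healthy 14.3%: 0.25 × 14.3 = 3.6, as stated. No sample size or power is given for Aim 3, so there is no Aim 3 figure to reproduce. Group size is 12 and 12 (section 9.2).

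**Elapsed time (flow sheet, section 4.1).** The MCC scan starts at cumulative minute 60. The post-albuterol scan ends at 184, which is 124 minutes later; the cough scan ends at 208, which is 148 minutes later. Taking the last 4 minutes of each as the image, the midpoints are 122 and 146. Interval: 146 − 122 = 24 minutes.

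**Rates.** Section 9.1 says an average clearance "represents the average clearance at the midpoint of each period of retention vs. time observation". So Ave60Clr is clearance at about 30 minutes and Ave120Clr at about 90.

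- Slow reading: 7.2% is the mild Ave120Clr. Mild rate (7.2 − 3.6)/60 = 0.06%/min. Severe unchanged, so rate 0.
- Untreated rate: mild 3.6/30 = 0.12%/min; severe 0.5/30 = 0.0167%/min.
- Doubled rate: mild 7.2/30 = 0.24%/min; severe 0.0167%/min. This assumes the albuterol effect lasts through the cough window, which the documents do not state.

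**Loss over 24 minutes with zero cough effect (percentage points).**

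| Reading | Mild | Severe | Gap |
|---|---|---|---|
| Slow | 0.06 × 24 = 1.4 | 0 | 1.4 |
| Untreated | 0.12 × 24 = 2.9 | 0.0167 × 24 = 0.4 | 2.5 |
| Doubled | 0.24 × 24 = 5.8 | 0.4 | 5.4 |

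Over the full 30 minutes named in section 9.3 the gaps are 1.8, 3.1 and 6.7.

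**False rejection.** I simulated the two-group t-test with 12 per group and no cough effect. Planned SDs were scaled to the window: mild 2/30 × 24 = 1.6 (untreated) and 4/30 × 24 = 3.2 (doubled); severe 0.25/30 × 24 = 0.2. For the slow reading the ratio of SD to mean was kept: 1.44 × 2/3.6 = 0.8. Independent noise was then added to each subject's change. Its SD is my assumption.

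| Reading | Added SD 2 | Added SD 4 |
|---|---|---|
| Slow | 37% | 13% |
| Untreated | 71% | 29% |
| Doubled | 98% | 78% |

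Nominal is 5%. With no added noise all three exceed 99%, but that leaves out image error and variation in cough.

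**Opposite effect.** In the untreated case with added SD 2, letting coughing clear 2 points more in the severe group brings rejection down to about 8%.

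**The variable as coded.** Ave120Clr sits at about 90 minutes, and Ave150Clr is not defined in section 9.1. If Ave150Clr stands for a time between 135 and 148 minutes, the difference spans 45 to 58 minutes of MCC. The untreated gap is then (0.12 − 0.0167) × 45 = 4.7 to (0.12 − 0.0167) × 58 = 6.0 points. That mismatch is a separate matter; the bias above remains after it is repaired.

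**The case against.** The best defence is one of weight. Aim 3 is tertiary and exploratory, is meant to characterise, and has no power claim. The synopsis describes the outcome as a change in MCC after coughing, which is not a claim to pure cough clearance. This limits how serious the point is. It does not remove it, because the section 9.3 text calls the quantity cough clearance, sets tests at 0.05 and predicts a direction.

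A second objection is that the size rests on assumptions. That stands. The documents give no measurement noise for the change, and the 7.2% figure can be read as a slow or a steep slope. The rejection rates are therefore a range. The shift in the mean does not depend on noise.

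Third, a correction adds noise and needs a model. That also stands, and is costed under the fix.

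Two stronger readings are tempting. A reader might infer that albuterol-stimulated MCC is the cause. The documents do not say how long albuterol acts on MCC, and the stimulus is not needed: the untreated mild rate alone gives 2.5 points. A reader might also infer that Aim 3 must confirm the prediction whatever coughing does. The figures do not support that: rejection is as low as 13% in the table, and about 8% with an opposite cough effect.

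**Conclusion.** The concern holds as a conditional bias. If the mild group has MCC and the severe group has almost none, as the plan expects, the uncorrected change favours the mild group by about 1.4 to 5.4 points over 24 minutes with no contribution from coughing. This assumes that the planned averages convert to constant rates, and the top of the range also assumes that a doubled rate persists to the cough image. If the mild group has no MCC, the bias is absent. Aim 3 is tilted toward its predicted result but not certain to give it. Since the outcome is exploratory and the remedy needs no new data, this should be changed before analysis; it does not threaten the primary aim.

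**What to change.** In section 9.3, Aim 3, add an MCC-corrected cough clearance: the retention change from the last MCC image to the cough image, minus the MCC expected over the same elapsed minutes, extrapolated from that subject's own post-albuterol images (about 70 to 120 minutes). Specify the extrapolation model in advance, for example log-linear in retention, with a linear fit as a sensitivity analysis. Test the corrected value against 0 and between groups, report the uncorrected change beside it, and base any statement about cough on the corrected value. In the synopsis and in section 4.1 (Outcome Measures), label the outcome *cough clearance after albuterol*.

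**Cost.** SAP wording and one calculation per subject from scheduled images, plus some precision.

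- *Noise.* With six images 10 minutes apart, the sum of squared time deviations is 1,750. The last MCC image is both the baseline and a point in the slope, so error variance in units of single-image variance is 2 + 24²/1750 + 2 × 24 × 25/1750 = 2 + 0.33 + 0.69 = 3.0, against 2.0 uncorrected. That is about 50% more variance; the SD goes from 1.41 to 1.74.
- *Model.* If clearance is exponential, k = −ln(1 − 0.036)/30 = 0.00122 per minute at the mild mean. A linear fit then predicts 2.61 points against a true 2.50 (untreated), or 5.01 against 4.57 (doubled). Averaged over the planned spread between subjects, the over-correction is about 0.1 to 0.5 points.
- *Persistence.* Any extrapolation assumes that the post-albuterol rate continues to the cough image. If it wanes, the correction takes away too much, which is another reason to show both values.

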2.3. Scientific Rationale

We have previously reported that PCD patients with *RSPH1* mutations have a milder pulmonary phenotype and better lung function than patients with PCD caused by other mutations [3]. Further, we demonstrated that although cilia lacking *RSPH1* beat in an abnormal, circular pattern, *Rspn1*^{-/-} mice exhibited a low level of MCC [13]. This is in contrast to *Dnaic1*^{-/-} mice, who exhibit essentially immotile cilia and a complete lack of MCC [14]. In this aim, we will test the hypothesis that PCD subjects with mutations in *RSPH1* and certain other mutations that have a milder phenotype [4, 11] maintain a low level of MCC that is likely responsible for their milder disease phenotype. In addition, we will test the hypothesis that stimulating ciliary beat frequency (CBF) with a beta-agonist will increase MCC in this patient group. These studies may result in the development of new personalized treatments for this rare disease.

3. Objectives

3.1. Specific Aim 1

To estimate how MCC measurements vary in subjects with PCD caused by mutations in genes associated with mild and severe clinical phenotypes relative to healthy subjects, and compare the 3 populations in terms of Average Clearance.

3.2. Specific Aim 2

To characterize the effect of a short acting beta agonist (SABA) on MCC subjects with PCD caused by mutations in genes associated with mild and severe clinical phenotypes and compare the 2 populations in terms of change in Average Clearance.

[figure not shown]
3.3. Specific Aim 3

To characterize effect of cough clearance in subjects with PCD caused by mutations in genes associated with mild and severe clinical phenotypes and compare the 2 populations in term of change in Average Cough Clearance.

4. Study Design

*Prior to
Enrollment*

Total N: Obtain informed consent over the phone or by virtual meeting. Screen potential participants by inclusion and exclusion criteria; obtain medical history, document over the phone or by virtual meeting.

Perform screening and spirometry. Perform mucociliary (MCC) baseline measurement. Continue MCC measurement after SABA administration. Repeat spirometry followed by controlled cough maneuvers to assess cough clearance (CC). Subject will rest for approximately 3.5 hours followed by a final MCC/CC static measurement, 6 hours (\pm 30 minutes) post initial scan.

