9.2. Description of the Study Cohort

The study cohort will consist of 12 PCD subjects with mutations in genes associated with a mild pulmonary phenotype (RSPH1, RSPH9, RSPH4a, or DNAH11) and 12 PCD subjects with mutations in genes associated with a more severe pulmonary phenotype (DNAH5, DNAI1, CCDC39, or CCDC40). A subject with mild pulmonary phenotype will typically have later onset of respiratory symptoms, better lung function, and milder bronchiectasis [4]. The age of patients will range between 12-90 years old. Eight healthy patients will be enrolled and undergo the same MCC protocol to obtain data for comparison. All subjects following the protocol will be included in the database. Subjects not

completing the protocol will be replaced. Baseline measurements of population (age, gender, race, FEV1) will be tabulated, for the whole population and per group (mild genotype, severe genotype, healthy) using mean and standard deviation and frequencies with percentages as appropriate. Data will be plotted in graphical figures including as histograms, bar plots, and scatter plots.

9.3.Aim-Specific Plans

Aim 1: To estimate how MCC measurements vary in PCD subjects with mutations in genes that are associated with mild or severe disease, relative to healthy subjects, and compare the 3 populations in term of Average Clearance.

Aim 1 is measuring MCC in PCD subjects having confirmed mutations in genes associated with a milder clinical phenotype and subjects with PCD caused by mutations in genes associated with a more severe clinical phenotype. These measurements will be reported as estimates of the means and standard deviations of Ave60Clr for each group, with associated confidence intervals. The baseline MCC in PCD subjects with “mild genotypes” and “severe genotypes” will be compared to healthy subjects. Our expected result is that subjects with mutations in genes associated with mild disease will display lower MCC rates than healthy subjects, and subjects with mutations in genes associated with severe disease will be even lower. For this comparison, we will use an ANOVA followed by multiple comparisons, using the Tukey Kramer correction. Then, to control for other possible sources of variations, age, gender and the initial deposition C/P will be added as covariates to PCD groups in a linear regression model on MCC.

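### Section 9.3 reads a non-significant mild-versus-severe comparison as evidence for another mechanism, although the plan's own rule calls such a result inconclusive

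*Combined protocol and SAP*

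**What the plan says.** Section 9.3 closes its aim-specific plans with a rule for every aim: two-sided tests at 0.05, and "Tests with p values above 0.05 will be considered inconclusive". The statistical part of the synopsis repeats it.

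The next paragraph of 9.3, on expected results, potential problems and alternatives, considers the case in which the mild and severe PCD groups are not found to differ. It says "this would suggest that the less severe clinical phenotype observed in some patients is not due to the maintenance of a low level" of MCC. It then calls this an important finding because "it would indicate that some other mechanism is responsible for the difference in phenotype".

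For Aim 1 the test is given as "we will use an ANOVA followed by multiple comparisons, using the Tukey Kramer correction". A regression adjusting for age, gender and initial C/P ratio follows. On estimation, the plan says "These measurements will be reported as estimates of the means and standard deviations of Ave60Clr for each group, with associated confidence intervals". Those intervals are for each group. None is named for the difference between the two PCD groups.

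**The concern.** One outcome, p above 0.05 for mild versus severe, has two prespecified meanings. Under the rule it settles nothing. Under the following paragraph it counts against the central hypothesis of section 2.3, that patients with milder genotypes "maintain a low level of MCC that is likely responsible for their milder disease phenotype".

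Failure to detect a difference supports its absence only if the data exclude differences large enough to matter. The plan does not say what size matters and does not specify an interval for the contrast. At stake is a published mechanistic conclusion drawn from a comparison that may simply have been too imprecise.

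**Working it through.** **The contradiction.** This part needs no arithmetic. The rule covers all tests in all aims, so it covers mild versus severe on Ave60Clr. The later paragraph is triggered by exactly the event the rule covers, and it sets no further condition, such as an interval excluding a stated difference.

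**Inputs for the size of the problem.**
- Section 9.6, Ave60Clr: healthy 14.3 ± 7.2, mild 3.6 ± 2, severe 0.5 ± 0.25. The ± values are not labelled and are taken as SDs. The expected mild-minus-severe difference is 3.6 − 0.5 = 3.1 points. The mild mean rests on the statement "we expect subjects with a mild genotype to average 25% of the MCC of healthy subjects".
- Section 9.2: 12 mild, 12 severe, and "Eight healthy patients will be enrolled".
- Data are simulated as normal, 200,000 runs (20,000 for the regression).

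**The plan's own figure.** Section 9.6 claims 80% power between all groups with n = 10. For a separate mild-versus-severe test:
- Averaged SD = √((2² + 0.25²)/2) = 1.425.
- n per group = 2 × (1.96 + 0.842)² × 1.425² / 3.1² ≈ 3.3, so 4.
- At n = 10, power is 0.998 (normal approximation) or 0.991 (Welch).

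So 10 per group is more than enough for a separate test, although n = 10 at 80% power is not itself reproduced. Under the named Tukey-Kramer procedure, power for this contrast at 10/10/10 is about 9%.

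**Tukey-Kramer at the enrolled 12/12/8.**
- Error df = 32 − 3 = 29; q(0.95; 3, 29) = 3.493.
- Expected MSE = (11 × 4 + 11 × 0.0625 + 7 × 51.84)/29 = 407.57/29 = 14.05. The healthy group supplies 362.88/407.57 = 89% of it.
- Half-width at that MSE = (3.493/√2) × √(14.05 × (1/12 + 1/12)) = 2.470 × 1.530 = 3.78. The simulated mean is 3.68, because the average root MSE is below the root of the average.
- Non-significant in 0.70 of trials when the true difference is 3.1.

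The typical half-width exceeds 3.1. Even an observed difference of exactly zero would therefore usually leave the planned difference inside the interval.

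**PCD groups only.** Proportion of trials that are non-significant. The regression has group plus three covariates (24 − 5 = 19 df), with the covariates assumed independent of group.

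| True difference | Mild SD | Welch | Regression |
|---|---|---|---|
| 3.1 | 2 (plan) | 0.002 | 0.006 |
| 3.1 | 3 (assumed) | 0.10 | 0.125 |
| 1.5 | 1.12 (assumed) | 0.015 | 0.028 |
| 1.5 | 2 (assumed) | 0.35 | 0.37 |
| 1.5 | 3 (assumed) | 0.65 | 0.65 |

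The 1.5-point difference is an illustration, not a value in the plan. The SD of 1.12 keeps the plan's mild SD-to-mean ratio: 2/3.6 = 0.56, times a mean of 0.5 + 1.5 = 2.0.

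**What a PCD-only null would exclude.** At the planning SDs the standard error is √(4/12 + 0.0625/12) = 0.582 with 11.3 df, so the Welch half-width is 2.193 × 0.582 = 1.28. An interval that just includes zero reaches at most about 2 × 1.28 = 2.6. It would exclude 3.1, but not necessarily a difference of 1.5 or 2.

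**The case against.** The best defence is that the governing rule is already right and is stated twice. The disputed paragraph is discussion text in conditional wording and sets no test or decision rule, so an analyst following the specified analysis would report an inconclusive result. The compliance statement also commits the study to statements critical of reliance on significance thresholds.

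The defence can add that the 70% comes from pooling the healthy variance, which this correction leaves unchanged, and that the paragraph does not name the test behind its null. If the null came from a PCD-only analysis, power at 3.1 points is so high that a null would be real evidence against the hypothesis as sized in section 9.6. The figures at 1.5 points rest on assumed inputs. The SD of 3 at a mean of 2.0 is a ratio of 1.5, far from the 0.50 to 0.56 seen throughout section 9.6. At the plan's own ratio the miss rate is only about 1.5%.

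Much of this stands. The 70% belongs to the choice of test, and the 1.5-point cases show only that the answer depends on an unknown SD. A PCD-only null would indeed speak against 3.1 points. But the paragraph does not confine itself to that analysis or that size of difference: it concludes that residual MCC is not the explanation at all. It also sits in the statistical section directly after the rule it contradicts. Conditional wording does not change the direction of the inference.

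**Conclusion.** The concern holds. The plan gives two incompatible readings of a non-significant mild-versus-severe result, and nothing in it supports the negative one. This follows from the text alone and does not depend on which test is used.

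The consequence varies with the analysis. Under the named Tukey-Kramer test, about 70% of trials would meet the condition for the negative reading although the plan's 3.1-point difference is true. Under a PCD-only analysis that figure is below 1% at the planning SD of 2 and about 10% to 13% at an assumed SD of 3. For a smaller true difference of 1.5 points it runs from about 1.5% to 65% across the assumed SDs. These figures assume normal data, ± values that are SDs, and 12/12/8 analysed.

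This should be corrected before results are read. Data collection, tests and sample size are not affected.

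**What to change.** The simpler option is to delete the last two sentences of the expected-results paragraph in section 9.3, from the point where it takes up the case of no detected difference. The inconclusive rule then stands alone.

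Alternatively, replace them with:

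> If the mild-versus-severe comparison is not significant, this will not by itself be taken as evidence that residual MCC does not explain the milder phenotype. The mild-minus-severe difference in Ave60Clr will be reported with a 95% CI that does not pool the healthy-group variance, and the conclusion will be limited to the differences that this interval excludes.

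Neither option needs a margin or a new decision rule. The cost is two sentences and, for the second option, one interval from data already collected. A null result could then be presented as evidence for another mechanism only as far as the interval allows.

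The second option has one drawback. At a true difference of 3.1 points, about 70% of trials would show a non-significant Tukey-Kramer result beside a Welch interval that excludes zero. That disagreement comes from pooling the healthy variance and should be settled separately in the Aim 1 text.
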